## Section 3: Statistical Principles

### 3.1 Confidence Intervals and P-values

Statistical significance will be set at  $\alpha=0.05$ . There is a single primary outcome. Prespecified secondary outcomes and subgroup analyses will be performed without adjustment for multiplicity. We will report measures of effect with 95% individual confidence intervals.

## 3.2 Adherence and protocol deviations

Adherence to the intervention is defined as study participants receiving the study product according to their allocated treatment arm for 75% of the study product deliveries during the first course of treatment (minimum of 3 deliveries during the first 6 months) and 75% of the study product deliveries during the second course of treatment (minimum of 3 deliveries during the second 6 months).

Deviations that may impact the analysis include:

1. Ineligible patients may be mistakenly randomized into the trial (randomization errors). While full source verification for participant eligibility is performed in accordance with the monitoring plan for the trial, the initial monitoring visit is scheduled to take place only after a participant has been randomized. Deviations arising from randomization errors will result in participant exclusion from the analysis population.
2. Patients may be incorrectly stratified during randomization (according to their 6MWD and type of PAH). If such cases arise, the participants will still be included in the analysis population.

All deviations will be monitored and recorded in the trial electronic data capture system (EDCS) on an on-going basis for the duration of the trial. The study sponsor will be immediately notified by the study monitors of any errors in randomizing ineligible participants, and the data will subsequently be entered into the protocol deviation eCRF to document the reason for the deviation along with the actions taken.

## 3.3 Analysis populations

The primary analyses will be by intent-to-treat but we will also conduct "per protocol" and "as treated" analyses.

Intent-to-treat analysis will include all randomized participants, including those who have not received a dose of the study product. Analysis will be based on the initial treatment assignment.

Per protocol analysis will include all randomized participants who have received at least 3 doses of the allocated study product during the first course of treatment (first 6 months), and at least 3 doses of the allocated study product during the second course of treatment (second 6 months), with all primary outcome measures having been captured.

As treated analysis will include all randomized participants who have received at least 1 dose of the study product. Analysis will be based on the actual treatment received rather than on the initial treatment assignment.

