- Physical examination by the principal investigator or sub-investigator
- Assessment of WHO functional class (see Appendix C)
- Assessment of adverse events and serious adverse events
- Vital signs
- Concomitant medication recording
- 12 lead ECG
- O₂ saturation (peripheral device)
- Laboratory tests: sodium, potassium, chloride, TCO₂, blood sugar, BUN, creatinine, calcium, magnesium, phosphorus, alkaline phosphatase, total bilirubin, CPK, troponin, AST (SGOT), ALT (SGPT), LDH, gamma GT, albumin, uric acid, CBC with differential, ESR, PT, PTT, INR (if warfarin sodium has been held for RHC procedure), BNP level, and CRP
- Additional blood samples for measurement of circulating biomarkers will be taken to be stored for no more than 15 years in the central biorepository at OHRI (no genetic testing will be performed)
- Urine pregnancy test for females with childbearing potential (to be done prior to administration of study product on the same day)
- Urine collection for routine and microscopic analysis

- 2D Echocardiogram with Doppler and saline contrast (as per echocardiography protocol)
- Cardiac MRI at sites where this is available (only for participants who are not on prostacyclin pumps and have no other exclusions for MRI such as claustrophobia) according to Cardiac MRI protocol
- PFTs [TLC, FVC, FEV₁/FVC, DLCO]
- Chest x-ray
- **6MWD test (for primary EP analysis)** and Borg dyspnea index (see Appendix D and E)
- Quality of Life Questionnaire SF-36 (see Appendix G)
- Out-patient right heart catheterization for hemodynamic assessment (BP, HR, RAP, RVP, PAP, mPAP, PAWP, PVR, SVR, CO, CI, SvO2)
 - Patients who are currently receiving anticoagulant therapy (warfarin sodium, NOAC) will be managed according to the standard procedure at participating sites
 - Cardiac output will be determined using the thermodilution (in triplicate) and/or Fick methods.

Administration of study product:

• As per section 7.1 (According to Study Product Delivery Protocol – Appendix H)

Post-treatment procedures:

• As per section 7.1 (According to Study Product Delivery Protocol – Appendix H)

7.5. Follow up/Treatment Visits: Months 7, 8 and 9 Post First Delivery of Study Product (±4 days; Can occur over 2 days)

Pre-treatment Procedures:

- Physical examination by the principal investigator or sub-investigator
- Assessment of WHO functional class (see Appendix C)
- Assessment of adverse events and serious adverse events
- Vital signs
- Concomitant medication recording

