**Secondary objectives:**

1. To compare the sustained effect of delivery of 4 vs. 8 doses of the cell therapy product on 6MWD at 12 months (i.e. Arm 2 vs. Arm 3)
2. To assess durability of any improvement in 6MWD at 3 vs. 9 months post last dose of cell therapy product (Arm 2 only)
3. To determine the incremental effect of delivery of 8 vs. 4 doses of the cell therapy product on 6MWD at 6 and 12 months (Arm 3 only)
4. To assess the cumulative effect of 4 doses of the cell therapy product on pulmonary vascular resistance at 6 months (Arms 2 and 3 vs. Arm 1)
5. To compare the sustained effect of delivery of 4 vs. 8 doses of the cell therapy product on pulmonary vascular resistance at 12 months (i.e. Arm 2 vs. Arm 3)
6. To assess durability of any improvement in pulmonary vascular resistance at 3 vs. 9 months post last dose of cell therapy product (Arm 2 only)
7. To determine the incremental effect of delivery of 8 vs. 4 doses of the cell therapy product on pulmonary vascular resistance at 6 and 12 months (Arm 3 only)
8. To assess effect of cell therapy on Quality of Life measured by the SF-36 at 6 months (Arms 2 and 3 vs. Arm 1)
9. To compare the sustained effect of delivery of 4 vs. 8 doses of the cell therapy product on Quality of Life measured by the SF-36 at 12 months (i.e. Arm 2 vs. Arm 3)
10. To assess the effect of cell therapy on a combined endpoint of death, or clinical worsening of pulmonary arterial hypertension at 6 and 12 months
11. To assess effect of cell therapy on measures of RV function by echocardiography at 6 and 12 months
12. To assess effect of cell therapy on RV function by Magnetic Resonance Imaging (MRI) at sites where this is available in patients with no contraindications for MRI (i.e. prostacyclin infusion pump, claustrophobia) at 6 and 12 months

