## 2.3 Sample Size

A total sample size of 39 participants (13 per arm) in an analysis of covariance using a planned comparison between the average of the two treatment arms versus control achieves 80% power to detect a minimally important mean difference of **50 meters** in the primary outcome (6MWD) using an F-test with a two-sided 5% significance level. The SAS procedure GLMPOWER was used to conduct the calculation (SAS Institute Inc. 2008. SAS/STAT® 9.2. User’s Guide. Cary, NC: SAS Institute Inc). The common standard deviation is assumed to be 85 and the correlation between baseline and 6 months is 0.80. These estimates are similar to those observed in our PHACeT trial where the standard deviation was 80 meters and the correlation between baseline and 6 month was 0.86. To account for 10% potential attrition, we will enroll and randomize 45 subjects (15 allocated to each arm).

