#### Primary Outcome

The primary outcome of this trial is 6-minute walk distance (6MWD) at 6 months.

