#### Analysis of Primary Outcome (6MWD at 6 months)

The primary analysis of our primary outcome, 6MWD assessed at baseline, one, two, three, four and six months, will use a general linear model with time (coded as a categorical variable) and group by time interaction as fixed covariates. As recommended for efficient analyses of longitudinal randomized controlled trials, baseline differences between the arms will be constrained through exclusion of the main effect for group. In addition to providing the unadjusted effect, we will adjust our estimate for the stratification factors (6MWD  $\leq 300$ m vs.  $> 300$ m and scleroderma APAH vs. all other eligible PAH categories), as well as age, gender and

baseline medication use (PDEVi and sGC stimulators vs. all other PAH-specific medications). The model will be estimated using Restricted Maximum Likelihood (REML), and degrees of freedom will be computed using the Kenward-Roger approach. Suitable covariance structures to account for correlation among repeated measures over time will be identified using likelihood ratio tests and information criteria (AIC and BIC). For the primary endpoint, the adjusted least square mean difference between the average of the two active treatment arms (Arms 2 and 3) versus placebo (Arm 1) at 6 months, together with 95% confidence interval, will be obtained and assessed at the two-sided 5% level of significance. Additional exploratory pairwise comparisons of least square mean differences at one, two, three, and four months will be conducted.

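### The single per-protocol set requires at least three course-2 doses, all given after the Month 6 walk, so it does not fit a 6-month per-protocol analysis of one four-dose course

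*SAP*

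**What the plan says.** SAP 3.3 makes intent-to-treat primary and adds per-protocol and as-treated analyses. Its per-protocol set needs at least three allocated doses in the first course "and at least 3 doses of the allocated study product during the second course of treatment (second 6 months"). The same sentence then adds a capture condition: "with all primary outcome measures having been captured". SAP 3.2 defines adherence on the same two-course basis, including "75% of the study product deliveries during the second course of treatment". Protocol 11.2 names a per-protocol analysis without defining it, and neither document has a set based on course 1 alone.

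On the outcome, SAP 5.1 states: "The primary outcome of this trial is 6-minute walk distance (6MWD) at 6 months". The primary objective (Protocol 2.1; SAP Section 1) concerns one course of four doses, comparing Arms 2 and 3 with Arm 1.

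On timing, Protocol 7.4 lists the "6MWD test (for primary EP analysis") among the pre-treatment procedures of the Month 6 visit. Protocol Appendix H places dosing at Months 0–3 and 6–9 and makes it the last procedure in the visit window.

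**The concern.** A per-protocol analysis of a 6-month outcome should describe participants who followed the treatment given up to 6 months. Here membership also depends on what happens from Month 6 onward. Someone with four of four course-1 doses and a valid Month 6 walk leaves the set if fewer than three course-2 doses follow. This can happen through doses counted as missed after the two-week rescheduling limit (Protocol 7.10), withdrawal or death (Protocol 9.5), or pregnancy (Protocol 9.7).

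Two things are at stake. The 6-month per-protocol result loses precision for reasons unrelated to the course under test. It also conditions on events after the outcome, and these could differ by arm because the course-2 product is cells, placebo and cells in Arms 1, 2 and 3.

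The capture clause raises a secondary point that is not sized here. It could mean the Month 6 walk alone, or every walk in the primary model ("6MWD assessed at baseline, one, two, three, four and six months"). It also makes per-protocol analyses of other outcomes depend on capture of the walk, for example secondary objective 4: "To assess the cumulative effect of 4 doses of the cell therapy product on pulmonary vascular resistance at 6 months".

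**Working it through.** **Timing.** Course 1 is Months 0, 1, 2 and 3. The primary walk is at Month 6, before dosing. Course 2 is Months 6, 7, 8 and 9. None of the four course-2 doses can precede the primary walk, yet three of the four are required for membership. One missed course-2 dose is tolerated; two or more exclude.

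**The plan's own figure.** Inputs from SAP 2.3: SD 85 m, baseline correlation 0.80, 13 per arm, difference 50 m, two-sided 5%.
- Residual SD = 85 × √(1 − 0.80²) = 51 m.
- Contrast = mean of Arms 2 and 3 minus Arm 1. SE = 51 × √(1/13 + 1/26) = 51 × √(1.5/13) = 17.3 m.
- Noncentral t with 39 − 3 − 1 = 35 degrees of freedom gives power 80.1%, which reproduces the stated 80%.

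**Precision under course-2 loss.** The documents give no rate, so 5–10% is assumed, with 20% as an upper bound. The plan's allowance, "To account for 10% potential attrition, we will enroll and randomize 45 subjects", belongs to the 6-month sample size and is not used as a course-2 rate. With SE = 51 × √(1.5/n):

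| Assumed loss | Lost of 39 | n per arm | SE (m) | 1.96 × SE (m) |
|---|---|---|---|---|
| 0% | 0 | 13 | 17.3 | 34.0 |
| 5% | 2.0 | 12.35 | 17.8 | 34.8 |
| 10% | 3.9 | 11.7 | 18.3 | 35.8 |
| 20% | 7.8 | 10.4 | 19.4 | 38.0 |

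**Bias with no true effect.** Let z be the standardised Month 6 residual and let logit(loss) = a − s·z, so that weaker walkers are more likely to be lost. The slope s is assumed to be 1 or 1.5, and a is solved so that marginal loss equals the assumed rate in every arm. The retained mean in a selected arm rises by d:

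| Loss | d, s = 1 (m) | d, s = 1.5 (m) | Size of bias, d/2 (m) |
|---|---|---|---|
| 5% | 2.4 | 3.3 | 1.2–1.7 |
| 10% | 4.6 | 6.2 | 2.3–3.1 |
| 20% | 8.8 | 11.6 | 4.4–5.8 |

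- Selection in Arms 1 and 3 only (course-2 cells): d/2 − d = −d/2.
- Selection in Arm 2 only (course-2 placebo): +d/2.
- Equal selection in all arms: d − d = 0.

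**Rejection rate with no true effect.** In 20,000 simulated trials per setting, starting from 13 per arm, the two-sided 5% rejection rate was 0.048–0.053 at 5–10% loss. At 20% loss it was 0.053–0.064 in the product-linked cases. The Monte Carlo standard error is about 0.0015.

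**The case against.** **The SAP does not say which endpoints the per-protocol set serves.** This is correct. Use for the 6-month outcome is an inference, though a strong one: the set is introduced beside the primary analyses, requires capture of the primary outcome, and has no alternative.

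**A two-course rule suits a 12-month, two-course trial and the Arm 2 versus Arm 3 objectives.** It does, and it should stay for analyses that use Month 12. That does not make it right for a 6-month analysis.

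**The bias is built from assumptions.** Also correct. The loss rate, the slopes and the arm-specific selection are assumed. The documents give no evidence that course-2 loss tracks Month 6 performance differently by arm, and the blind is kept for all 12 months. The timing mismatch needs no such assumption.

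**Emergency unblinding is a poor example of wrongful exclusion.** Agreed. Protocol 9.1 itself classes such a participant as off-protocol, so that route is not relied on here.

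**The likelihood model could also accommodate a missing Month 6 value, so a capture condition is not strictly needed.** This is fair. The fix keeps the SAP's existing condition and limits it to the values being compared.

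A reader might infer that the primary result is compromised or that the false-positive risk rises materially. Neither is supported. The primary analysis is intent-to-treat, and the rejection rate stays near 5% at 5–10% loss. Nor does the as-treated set fill the gap, because it requires only one dose.

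**Conclusion.** The point holds as a mismatch of definition and timing. The only per-protocol set conditions on doses given after the primary walk, so it does not represent adherence to the single course named in the primary objective. Its use for the 6-month outcome is the plain reading, not stated SAP wording.

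The consequence is confined to the 6-month per-protocol results. At an assumed 5–10% course-2 loss, the SE increases by 0.5–0.9 m (17.8 − 17.3 and 18.261 − 17.324). Bias runs from about zero to 3.1 m in either direction, depending on the assumed selection. No trial conclusion is shown to change. Severity is minor to moderate. Confidence is high on the definition and timing; the sizes are conditional on the stated assumptions.

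**What to change.** Before database lock and unblinding, amend SAP 3.3 and 3.2:

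- **6-month analyses:** at least three of the four allocated course-1 doses, and capture of the 6-month value of the outcome being analysed, regardless of course-2 events. State that a missed walk at Months 1–4 does not exclude a participant, since the repeated-measures model uses the remaining data.
- **12-month between-arm analyses:** keep the two-course dose rule, with capture of the 12-month value of the outcome being analysed.
- **6-to-12-month within-arm comparisons (durability in Arm 2, incremental effect in Arm 3):** keep the two-course dose rule, with capture of both the 6- and 12-month values, because the contrast uses both.
- **SAP 3.2:** split the adherence definition by course in the same way.

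The cost is SAP wording and one extra population flag. No new data are needed. Made after unblinding, the same change could look data-driven.

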## Section 4 – Trial Population

### 4.1 Eligibility

Referrals for screening will be made by physicians who follow patients for clinical management of PAH at participating SAPPHIRE trial sites, all of which are specialized pulmonary hypertension clinics. Health records will be reviewed in compliance with the Federal Personal Information Protection and Electronic Documents Act (PIPEDA), provincial privacy laws, and local hospital privacy policies.

The research consent process will be initiated at the research site for potential participants who appear to be eligible based on available clinical information. For potential participants who wish to proceed with the trial and who provide written consent, research investigations will then commence. Screening investigations will be completed as outlined in the schedule of assessments in **Appendix B**.

#### **Inclusion Criteria:**

Patients participating in the study must meet ALL of the following inclusion criteria:

- Age  $\geq$  18 years,  $\leq$  80 years
- Established diagnosis of PAH due to the following:
  - Idiopathic or heritable PAH;
  - Scleroderma associated PAH (limited or diffuse);
  - Drugs (anorexigens) or toxins;
  - Congenital heart defects (atrial septal defects, ventricular septal defects, and patent ductus arteriosus) repaired  $\geq$  1 years
- WHO functional class II, III, or IV on appropriate stable therapy for PAH for at least 3 months prior to the screening period and up until randomization, apart from modification of anticoagulant or diuretic dosages, or small adjustments in prostaglandin dose that are considered by the Investigator to be consistent with stable parenteral therapy.
- Able to walk unassisted (oxygen use allowed). Aids for carrying oxygen (such as a wheel chair or walker) are permitted provided they are not also required as mobility aids.
- An average 6-Minute Walk Distance (6MWD) of  $\geq$  125 meters and  $\leq$  440 meters on two consecutive tests during the Screening period
- Previous diagnostic right heart cardiac catheterization (RHC) at the time of PAH diagnosis with findings consistent with PAH: specifically, mean pulmonary arterial pressure (mPAP)  $\geq$  25 mmHg (at rest); pulmonary capillary wedge pressure (PCWP) (or left ventricular end diastolic pressure)  $\leq$  15 mmHg, and pulmonary vascular resistance (PVR)  $>5$  WU. If repeat testing has occurred since initial diagnosis, the most recent results should be used.
- Echocardiography performed within 12 months prior to the Screening Period confirming a left atrial volume index (LAVI) of  $\leq$  34 ml/m^2 and the absence of any clinically significant left heart disease including evidence of more than mild left-sided valvular heart disease, systolic or diastolic left ventricular dysfunction

- Ventilation and perfusion (VQ) nuclear scan performed as part of the initial workup to establish the diagnosis of PAH showing absence (i.e. low probability) of pulmonary embolism. If repeat testing has occurred since initial diagnosis, the most recent results should be used.
- Pulmonary function tests conducted within 2 years prior to the Screening Period to confirm: total lung capacity (TLC)  $\geq$  65% the predicted value; and forced expiratory volume at one second (FEV1) of  $\geq$  65% the predicted value
- Must have a resting arterial oxygen saturation (SaO2)  $\geq$  88% with or without supplemental oxygen as measured by pulse oximetry at the Screening Visit
- Must not be enrolled in an exercise training program for pulmonary rehabilitation within 3 months prior to the Screening Visit and must agree not to enroll in an exercise training program for pulmonary rehabilitation during the Screening Period and the first 6 months of the study. Participants enrolled in an exercise program for pulmonary rehabilitation 3 months prior to screening may enter the study if they agree to maintain their current level of rehabilitation for the first 6 months of the study
- Women of child-bearing potential (defined as less than 1 year post-menopausal and not surgically sterile) must be practicing abstinence or using two highly effective methods of contraception (defined as a method of birth control that results in a low failure rate, i.e., less than 1% per year, such as approved hormonal contraceptives, barrier methods [such as a condom or diaphragm] used with a spermicide, or an intrauterine device). Subjects must have a negative  $\beta$ -hCG pregnancy test during the Screening period and negative urine pregnancy test results at all other study visits
- Must be willing and able to comply with study requirements and restrictions.

#### **Exclusion Criteria:**

Patients will not be included in the study if ANY of the following exclusion criteria are present:

- Pregnant or lactating
- PAH related to any condition not covered under inclusion criteria, including but not limited to pulmonary venous hypertension, pulmonary veno-occlusive disease, pulmonary capillary hemangiomatosis, or chronic thromboembolic pulmonary hypertension
- Evidence of more than mild interstitial lung disease on Chest CT within the last 5 years (last 3 years for patients with scleroderma associated PAH)
- Treatment with an investigational drug, device or therapy within 3 months prior to the screening period or is scheduled to receive an investigational drug, device or therapy during the course of the study
- Any musculoskeletal disease or any other disease that would significantly limit ambulation
- Unrepaired or recently repaired (< 1 year) congenital systemic-to-pulmonary shunt other than patent foramen ovale
- Patients having three or more of the following four AMBITION study HFpEF risk factors will be excluded:

---

- BMI  $\geq 30 \text{ kg/m}^2$ ,
- History of essential hypertension,
- Diabetes mellitus (any type)
- Historical evidence of significant coronary artery disease (CAD) by ANY ONE of the following:
  - History of MI
  - History of PCI
  - Prior coronary angiography evidence of CAD (>50% stenosis in  $\geq 1$  vessel)
  - Previous positive Stress Test
  - Previous CABG
  - Stable angina
- Creatinine clearance  $<30 \text{ ml/min}$  (using the Cockcroft-Gault formula) or requires hemodialysis
- Inability to undergo the apheresis procedure due to poor venous access or laboratory tests that are not within acceptable ranges (not including INR for patients on Coumadin)
- Childs-Pugh class C liver cirrhosis
- Previous atrial septostomy
- Any other clinically significant illness or abnormal laboratory values (measured during the screening period) that, in the opinion of the Investigator, might put the subject at risk of harm during the study or might adversely affect the interpretation of the study data
- Anticipated survival less than 1 year due to concomitant disease
- History of cancer in the past 5 years (except for low grade and fully resolved non-melanoma skin cancer)
- Results during screening consistent with current infection with HIV, Hepatitis B(HBV) or C(HCV), human T-cell lymphotropic virus (HTLV- I/II) or syphilis
- Systemic arterial systolic blood pressure  $< 85 \text{ mm Hg}$
- Known allergy to gentamicin or amphotericin
- Patients who have participated in any gene therapy study or an angiogenic growth factor protein study
- Patients unable to provide informed consent and comply with the visit schedule.

